1. INTRODUCTION

This is a Phase 2, open-label, 2-cohort study designed to evaluate the efficacy and safety of 2 INCB050465 treatment regimens in relapsed or refractory MCL participants previously treated either with or without a BTK inhibitor.

Section 1 of the Protocol provides a detailed description of the investigational product, target participant population, rationale for doses to be examined, and potential risks and benefits of treatment with INCB050465.

The purpose of this SAP is to provide details of the statistical analyses that have been outlined in the Study INCB 50465-205 Protocol. The scope of this plan includes the interim and final analyses that are planned and will be executed by the Department of Biostatistics or designee,

[REDACTED]

2. STUDY INFORMATION, OBJECTIVES, AND ENDPOINTS

2.1. Protocol and Case Report Form Version

This SAP is based on INCB 50465-205 Protocol Amendment 7 dated 30 JAN 2020 and CRFs approved 26 NOV 2018. Unless superseded by an amendment, this SAP will be effective for all subsequent Protocol amendments and CRF versions.

2.2. Study Objectives and Endpoints

[Table 1](#) presents the objectives and endpoints.

Table 1: Objectives and Endpoints

Objectives	Endpoints
Primary	
To assess the efficacy of INCB050465 in terms of ORR in participants with MCL that is relapsed or refractory after at least 1 but no more than 3 prior systemic treatment regimens.	ORR defined as the percentage of participants with a CR or PR as determined by IRC assessment of response according to CT-based response criteria for lymphomas (Cheson et al 2014).
Secondary	
To assess DOR.	DOR defined as the time from first documented evidence of CR or PR until disease progression or death from any cause among participants who achieve an objective response, as determined by radiographic disease assessment provided by an IRC.
To assess CRR.	CRR defined as the percentage of participants with a CR as defined by response criteria for lymphomas (Cheson et al 2014), as determined by an IRC.
To assess PFS.	PFS defined as the time from the date of the first dose of study treatment until the earliest date of disease progression, as determined by radiographic disease assessment provided by an IRC, or death from any cause.
To assess OS.	OS defined as the time from the date of the first dose of study treatment until death from any cause.
To assess the best percentage change in target lesion size.	Best percentage change in target lesion size from baseline, where target lesion size is measured by the sum of the product of diameters of all target lesion sizes.
To characterize the safety and tolerability of INCB050465.	Safety measured by AEs, 12-lead ECGs, chemistry and hematology laboratory values, vital signs, and physical examinations.

3. STUDY DESIGN

This is a Phase 2, open-label, 2-cohort study designed to evaluate the efficacy and safety of 2 INCB050465 treatment regimens in relapsed or refractory MCL previously treated either with or without a BTK inhibitor (see [Figure 1](#)). Participants will be allocated to Cohort 1 or Cohort 2 as follows:

- Cohort 1: Participants have previously received ibrutinib
- Cohort 2: Participants have not previously received a BTK inhibitor

However, Cohort 1 was closed to further enrollment per Protocol Amendment (Version) 7. Cohort 1 and Cohort 2 will have separate designs, conduct, and analyses. Participants enrolled in Cohort 1 and the first 60 participants in Cohort 2 will be further allocated to 1 of 2 study treatment regimens as follows:

[figure not shown]
- Treatment A: INCB050465 20 mg QD for 8 weeks followed by 20 mg once weekly
- Treatment B: INCB050465 20 mg QD for 8 weeks followed by 2.5 mg QD

An interim futility analysis is planned for each of the cohorts when 30 participants have been treated and evaluated for response or have permanently discontinued study treatment because of disease progression, withdrawal of consent, or death. Cohort 1 will be terminated for futility if ≤ 3 of the 30 participants responded (ie, CR or PR) based on assessments provided by the IRC. Cohort 2 will be terminated for futility if ≤ 10 of the 30 participants have responded (ie, CR or PR) based on assessments provided by the IRC.

To better understand the safety and efficacy of INCB050465, a total of 70 additional participants (30 participants in Cohort 1 and 40 participants in Cohort 2) will be enrolled into 1 of the 2 treatment regimens being evaluated in this study. The treatment regimen will be selected after enrollment is completed for either Cohort 1 or Cohort 2 (ie, 60 participants enrolled) and after evaluation of emerging safety and efficacy data from this and other monotherapy studies of INCB050465 in non-Hodgkin lymphoma. Once a treatment regimen is selected, the nonselected treatment regimen will be closed to further enrollment. Participants receiving the nonselected treatment regimen may switch to the selected treatment regimen or remain on their current treatment regimen, provided they have not met study-treatment withdrawal criteria and there are no safety concerns for their current treatment regimen. There will be no rebaselining for participants who switch treatment regimens and all participants will continue to follow the same assessment schedule.

Participants will receive treatment until disease progression, death, unacceptable toxicity, or consent withdrawal, whichever occurs first. Participants will be evaluated for ORR by an IRC and followed for DOR, PFS, and OS.

Figure 1: Study Design of INCB 50465-205

EOT = end of treatment; MCL = mantle cell lymphoma; QD = once daily

^a A futility analysis will be performed for each of the cohorts when the first 30 patients in each cohort have been treated and evaluated for response (see Section 9.6). Final analysis will occur when all subjects in the respective Cohort have received at least 1 postbaseline disease assessment, or have progressed, withdrawn from the study, or died.

^b Cohort 1 will be closed to further enrollment by Protocol Amendment 7 with approximately 50 subjects enrolled.

^c Subjects who discontinue study treatment for a reason other than disease progression will continue with disease assessments by radiologic imaging per the Schedule of Assessments.

^d Every 12 weeks by clinic visit, telephone, or e-mail.

^e Urine pregnancy and dispensing of study treatment will occur every 4 weeks.

3.1. Randomization

Not applicable.

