4. INVESTIGATIONAL PLAN

4.1. Overall Study Design

This is a Phase 2, open-label, 2-cohort study designed to evaluate the efficacy and safety of 2 INCB050465 treatment regimens in relapsed or refractory MCL previously treated either with or without a BTK inhibitor (see Figure 1). A total of approximately 190 subjects were planned to be enrolled across 2 cohorts. Cohort 1 will be closed to further enrollment by Protocol Amendment 7 with approximately 50 subjects enrolled. The estimated total number of subjects to be enrolled in the study is approximately 150.

Subjects with MCL who have received at least 1 but no more than 3 prior systemic treatment regimens will be screened for eligibility. Subjects will be allocated to Cohort 1 or Cohort 2 as follows:

- Cohort 1: Subjects have previously received ibrutinib
- Cohort 2: Subjects have not previously received a BTK inhibitor

Cohort 1 and Cohort 2 will have separate designs, conduct, and analyses.

The first 60 subjects in each cohort who meet the eligibility criteria will be randomly allocated to 1 of 2 study treatment regimens through the IWRS (see Section 5.1):

- Treatment A: INCB050465 20 mg QD for 8 weeks followed by 20 mg once weekly
 - Subjects in Cohort 1 receiving Treatment A will be referred to as Cohort 1A
 - Subjects in Cohort 2 receiving Treatment A will be referred to as Cohort 2A
- Treatment B: INCB050465 20 mg QD for 8 weeks followed by 2.5 mg QD
 - Subjects in Cohort 1 receiving Treatment B will be referred to as Cohort 1B
 - Subjects in Cohort 2 receiving Treatment B will be referred to as Cohort 2B

To better understand the safety and efficacy of INCB050465, a total of 70 additional subjects (30 subjects in Cohort 1 and 40 subjects in Cohort 2) will be enrolled into one of the 2 treatment regimens (A or B) being evaluated in this study. The treatment regimen will be selected after enrollment is completed for either Cohort 1 or Cohort 2 (ie, 60 subjects enrolled) and after evaluation of emerging safety and efficacy data from this and other monotherapy studies of INCB050465 in NHL. Once a treatment regimen is selected, the nonselected treatment regimen will be closed to further enrollment. Subjects receiving the nonselected treatment regimen may

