5. TREATMENT

5.1. Treatment Assignment

5.1.1. Subject Numbering and Treatment Assignment

Study sites will enter subject demographic and baseline data into the IWRS in order to receive a subject number and random treatment allocation.

All subject numbers will be 6 digits; the first 3 digits will be the site number, and the last 3 digits will be the subject's number. This subject number will be maintained throughout the study and will not be reassigned. Subjects who withdraw consent or discontinue from the study after being assigned a subject number will retain their initial number.

Site staff will contact the IWRS to allocate the subject to treatment assignment and obtain the initial study treatment assignment. The investigator or designee will select the assigned bottles of study treatment from their stock that correspond to the number provided by the IWRS and dispense the study treatment to the subject. All subsequent dispensing of study treatment should follow this process. Refer to the IWRS Manual for detailed information.

If a subject is mistakenly given a bottle of study treatment that is not the bottle assigned by the IWRS, the IWRS help desk must be notified immediately. The reason for the misallocation of the study treatment must be documented by the study site and reported to the IRB/IEC.

For subjects who signed an ICF but are not allocated study treatment and for subjects who are allocated study treatment but were not treated, refer to the eCRF Completion Guidelines for instruction on which eCRFs to complete.

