9.4.1.3. Other Efficacy Analyses

Analyses of ORR, DOR, CRR, and PFS as reported by the investigator will be summarized as described above.

Analyses of ORR, DOR, CRR, PFS as determined by IRC and OS will also be summarized by treatment regimens (A or B) within each cohort.

Health-related quality of life scales as well as change and percentage change from baseline will be summarized descriptively by visit.

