5.2. Treatment Groups

This is a Phase 2, open-label, 2-cohort study. All analyses will be conducted independently for Cohort 1 and Cohort 2, and there will not be multiplicity adjustment between the cohorts. Within each cohort, there will not be any statistical comparison between the treatment groups.

For analysis purposes, the 20 mg once weekly dosing period and the 2.5 mg QD dosing period in Group A and Group B, respectively, are considered maintenance dosing periods. Within each of the 2 cohorts, data will be presented in summary tables by actual received treatment regimen and combined, with an exception for participants who cross over to the selected treatment regimen after the start of the maintenance dosing period.

For participants who cross over from the initially assigned treatment regimen to the selected treatment regimen, if the crossover happens on/prior to the start of the maintenance dosing period then the participant will be summarized, according to the actual received treatment, in the selected treatment regimen; otherwise, the participant will be summarized in:

- A separate treatment regimen (ie, Crossover) for the safety summaries during the maintenance dosing period (eg. summaries of TEAEs and exposure).
- The initially assigned treatment regimen for all other summaries.

Per Protocol Amendment (Version) 7, Cohort 1 was closed to further enrollment. If the number of participants who have enrolled in Cohort 1 is relatively few, summary tables will be replaced with listings.

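### Cohort 2's by-regimen summaries pool randomised and later non-randomised Treatment B participants, while SAP 3.1 and Protocol 5.1.2 say that randomization does not apply

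*SAP*

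**What the plan says.** **Allocation.** Protocol 4.1 states: "The first 60 subjects in each cohort who meet the eligibility criteria will be randomly allocated to 1 of 2 study treatment regimens". Protocol 5.1.1 has sites enter data in the IWRS "in order to receive a subject number and random treatment allocation". Protocol 5.1.2, Randomization and Blinding, nevertheless declares the topic inapplicable, and SAP 3.1 reads "Not applicable". SAP 3 describes the same step without the word random: "Participants enrolled in Cohort 1 and the first 60 participants in Cohort 2 will be further allocated to 1 of 2 study treatment regimens". Neither document gives an allocation ratio, stratification factors or a block scheme.

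**Expansion.** Under SAP 3, the additional participants (40 in Cohort 2) "will be enrolled into 1 of the 2 treatment regimens being evaluated in this study". The SAP 11.2 change note for Section 6.4 records that B was selected.

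**Reporting.** Protocol 9.4 pools A and B for primary and secondary efficacy. Protocol 9.4.1.3 adds that ORR, DOR, CRR, PFS and OS "will also be summarized by treatment regimens (A or B) within each cohort". SAP 5.2 groups participants by the regimen actually received. For switchers it says: "if the crossover happens on/prior to the start of the maintenance dosing period then the participant will be summarized" in the selected regimen. Later switchers form a separate Crossover group in maintenance-period safety summaries and otherwise stay in their initial regimen. SAP 3.2 and 5.2 rule out any statistical comparison of the regimens.

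**The concern.** Open-label conduct makes blinding inapplicable; it does not make randomization inapplicable. Once the SAP treats the allocation as non-random, nothing in it protects the randomised structure. In Cohort 2 the result is an A column drawn from the randomised phase, less any early switchers, beside a B column that mixes three groups: randomised B participants, later participants who could only enter B, and early switchers from A.

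The columns therefore differ in calendar time and selection. At a common data cutoff they also differ in length of follow-up. Both regimens give the same treatment for the first 8 weeks, so the outcomes most exposed are the time-dependent ones: DOR, PFS and maintenance-period safety.

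This matters because Protocol 1.5 says the two regimens are meant to show whether AEs leading to withdrawal can be reduced while response is maintained. Readers will compare adjacent columns for that purpose whether or not a test is planned.

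**Working it through.** **1. Cohort size, and a check that the pooled analysis is not at issue.** 60 + 40 = 100, as SAP 3.3 states. With the planned exact 95% CI, a lower bound of at least 40% needs at least 51 responders in 100. At a true ORR of 60% that has probability 0.973 (0.971 allowing for the futility stop), against approximately 97% stated. The figure is reproduced and does not depend on the split between A and B.

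**2. Composition of column B in Cohort 2.** Let n_B be the number randomised to B among the first 60. The non-randomised share is 40/(n_B + 40). The ratio is an assumption, so a range is shown, with early switchers left out because their number is not given.

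| Assumed A:B | A | Randomised B | Column B | Not randomised |
|---|---|---|---|---|
| 1:2 | 20 | 40 | 80 | 40/80 = 50% |
| 1:1 | 30 | 30 | 70 | 40/70 = 57% |
| 2:1 | 40 | 20 | 60 | 40/60 = 67% |

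**3. Effect on the B estimate.** If true ORR in the later 40 differs by d points from that in the randomised B participants, column B shifts by (share × d). At 1:1, 40/70 × 10 = 5.7 points for d = 10, and 40/70 × 20 = 11.4 points for d = 20. For d = 10 the range over the table is 0.50 × 10 = 5.0 to 0.67 × 10 = 6.7 points. The values of d are illustrative; the documents give none.

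**4. Precision of a randomised-only view.** The approximate 95% half-width for the A minus B difference in ORR, at 60% in each, is 1.96 × √(0.24/30 + 0.24/n_B column).
- Randomised only, 30 and 30: ±24.8 points.
- As planned, 30 and 70: ±21.0 points.

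Restriction therefore widens the interval by 24.8 − 21.0 = 3.8 points and removes the mixing.

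**5. Is the split available elsewhere in the plan?** The subgroup list in SAP 7.3.2 has no factor for enrolment phase. The tables, figures and listings in SAP Appendix A include none limited to the first 60 of Cohort 2. Tables 2.4.1 to 2.4.8 and the sensitivity analyses in SAP 7.3.1, 7.4.1, 7.4.2 and 7.4.3 deal only with participants who switched after maintenance began.

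**6. Cohort 1.** Protocol 4.1 closes it at about 50, below the 60 that come before the expansion, and SAP 3 describes all its participants as allocated to A or B. The 30-participant expansion therefore does not arise. Two exceptions remain: early switchers are reclassified, and anyone enrolled after B was selected could not have entered A, because the trigger is 60 enrolled in either cohort. At 25:25 and an ORR of 28%, the half-width is 1.96 × √(0.28 × 0.72 × 2/25) = ±24.9 points.

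**The case against.** The strongest reply is that the plan disclaims what is being asked for. Protocol 4.2 and SAP 3.2 exclude between-regimen comparison, the primary objective is the ORR of the drug, and primary and secondary efficacy are pooled. That stands for inference: no test is affected, and neither is the pooled ORR. It does not settle how descriptive columns should be built when comparable ones are already in hand.

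Second, late switchers are already handled by the Crossover group and the sensitivity analyses, and counting early switchers under the regimen they received is a defensible as-treated rule. This also stands, and it limits the remedy. Assigning every TEAE to the randomised regimen would place late switchers' events on B under A, which the Crossover group avoids in the maintenance-period summaries.

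Third, the randomised set is imprecise and, for DOR, PFS and maintenance safety, is itself affected by one-way switching in an open-label trial. It is better described as comparable at allocation than as unbiased throughout.

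A reader might go further and infer that the randomised evidence is shown nowhere in the trial. That is not supported: Cohort 1's by-regimen tables come close to it, although SAP 5.2 allows listings in place of tables if numbers are few. A reader might also infer a definite selection bias in B's ORR. If the choice had rested on ORR alone, with 30 complete results per regimen and a true ORR of 60% in both, the bias would be about 5.0 points in the 30 and 5.0 × 30/70, or roughly 2.2, in the 70. But SAP 3 bases the choice on emerging safety and efficacy data from this and other studies, so those figures are an upper-end scenario and not an estimate.

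**Conclusion.** The point holds for Cohort 2. The documents contradict themselves on whether allocation is random, and the planned by-regimen summaries mix randomised and non-randomised participants in column B without any table that separates them. Under assumed 1:1 allocation, 57% of that column is not randomised (50% to 67% for A:B from 1:2 to 2:1). A 10-point ORR difference in the later participants would move it by about 5.7 points; whether such a difference exists is unknown.

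The damage is confined to descriptive by-regimen results and to the support they lend the regimen choice. It would be wrong to read this as a flaw in the pooled primary ORR. Nor do the documents allow a numerical bias in AE incidence to be stated, since they give neither AE rates nor follow-up by enrolment phase.

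**What to change.** 1. In SAP 3.1 and Protocol 5.1.2, replace the present entry with the random allocation actually used: the first 60 per cohort through the IWRS, the ratio, and any stratification. State separately that the study is open-label.
2. For Cohort 2, add descriptive by-regimen summaries of ORR, CRR, DOR and PFS limited to randomised participants, each in the regimen to which they were randomised. Keep the planned sensitivity analyses that censor DOR and PFS at crossover.
3. Show the non-randomised B expansion participants in their own column for efficacy and safety. This also gives an estimate of B from participants whose data played no part in selecting it.
4. For TEAEs, limit the A and B columns to randomised participants, but keep the SAP's separate Crossover group in the maintenance period so that late switchers' events are not assigned to A.
5. Label the A and B results as descriptive and note their imprecision, about ±25 points on the ORR difference at 30:30.

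The cost is SAP and Protocol wording and some extra table columns. No new data are needed and the pooled primary analysis does not change.

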3.2. Control of Type I Error

There will not be any statistical comparison between Cohort 1 and Cohort 2. Within each of the 2 cohorts, there will not be any statistical comparison between the 2 treatment regimens, and 2-sided 95% CIs will be reported for all analyses when appropriate.

Within each cohort, no adjustment for alpha spending is considered as there are no plans to stop the study early for overwhelming efficacy. An IDMC will be assembled to monitor safety data and study conduct on a regular and ongoing basis during the study. The IDMC will also be charged with evaluating interim futility results. See Section 10 for details regarding interim analyses conducted in this study.

3.3. Sample Size Considerations

Cohort 1 was closed to further enrollment with Protocol Amendment (Version) 7.

The study will enroll up to 100 participants into Cohort 2. If the true ORR is 60%, then there is approximately 90% or 97% probability of observing the lower bound of the 95% CI of $ORR \geq 40\%$ with 60 or 100 participants, respectively.

3.4. Schedule of Assessments

See Protocol Amendment 7 dated 30 JAN 2020 for a full description of all study procedures and assessment schedules for this study.

4. DATA HANDLING DEFINITIONS AND CONVENTIONS

4.1. Scheduled Study Evaluations and Study Periods

4.1.1. Day 1

Day 1 is the date that the first dose of study drug (INCB050465) is administered to the participants.

4.1.2. Study Day

If a visit/reporting date is on or after Day 1, then the study day at the visit/reporting date will be calculated as

$$\text{Day \#} = (\text{Visit/Reporting Date} - \text{Day 1 date} + 1).$$

If the visit/reporting date is before Day 1, then the study day at the visit/reporting date will be calculated as

$$\text{Day \#} = (\text{Visit/Reporting Date} - \text{Day 1 date}).$$

A study day of -1 indicates 1 day before Day 1.

4.1.3. Baseline Value

Baseline is the last nonmissing measurement obtained before the first administration of INCB050465, unless otherwise defined.

When scheduled assessments and unscheduled assessments occur on the same day and time of the assessment or time of first dose is not available, use the following convention to determine baseline:

- If both a scheduled and an unscheduled visit are available on the day of the first dose and the time is missing, use the scheduled assessment as baseline.
- If all scheduled assessments are missing on the day of the first dose and an unscheduled assessment is available, use the unscheduled assessment as baseline.

4.1.4. Handling of Missing and Incomplete Data

In general, values for missing data will not be imputed unless methods for handling missing data are specified in this section or relevant sections. The original reported dates collected on the

eCRF should be used in all relevant listings. The following rules will be used for handling missing or partial dates for analyses requiring dates.

When calculating time since initial diagnosis of cancer, partial diagnosis date will be handled in the calculation as follows:

- If only the day is missing, then the first day of the month will be used.
- If both the month and day are missing, then 01 JAN will be used.
- Otherwise, the time since diagnosis will not be calculated.

When the date of the last dose is used in deriving variables such as duration of treatment or TEAE flag, missing or partial date of last dose will be handled in the calculation as follows:

- If only the day is missing, then the earlier date of the last day of the month or the date that the participant discontinued treatment will be used.
- If both the month and day are missing, then the earlier date of 31 DEC of the year or the date that the participant discontinued treatment will be used.
- Otherwise, the date that the participant discontinued treatment will be used as the date of the last dose.

When calculating DOR, PFS, and OS, a partial date of death will be handled in the calculation as follows:

- If mmyyyy for the last known alive date = mmyyyy for the death date, then the day after the last known alive date will be used.
- If mmyyyy for the last known alive date < mmyyyy for the death date, then the first day of the death month will be used.
- Otherwise, the partial death date will not be handled.

When calculating time to onset or duration of a TEAE, a partial or missing AE onset/end date will be handled in the calculation as follows:

- If only the day is missing, then the first day of the month or Day 1, whichever is later, will be used as the onset date; the earlier date of the last day of the month or the date that the participant discontinued study or died will be used as the end date.
- If both the month and day are missing, then 01 JAN or Day 1, whichever is later, will be used as the onset date; the earlier date of 31 DEC or the date that the participant discontinued study or died will be used as the end date.
- Otherwise, Day 1 will be used as the onset date, and the missing end date will not be handled.

